**2. If this is a multi-Center Project, what is the maximum anticipated number of subjects across all sites?**

**3. Provide justification for the sample size by explaining how you arrived at the expected number of participants and why this number is adequate for answering the research questions:**

Sample: A non-probability sampling (convenience sampling) method will be adopted to allow reach all potential participants. The team members will approach potential respondents at Islamic centers to participate in this study. The inclusion criteria include women aged  $\geq 18$  years who speak English, self-identify as Muslim, and have not participated in our pilot study before. The exclusion criteria are any participants who participated in our pilot study or are unable to provide valid consent (e.g., developmental disability).

Qualitative analysis side: to develop the education material we will recruit 10 female participants above 18 years old who identify as Muslim to participate in the design of the religiously tailored and culturally appropriate education materials for the intervention. First the focus group will help select the targets of the proposed education and the content to achieve each target (design). As a next step the focus group will focus on the formatting of the material, including basic usability testing (refine). Based on information from these sessions we will finalize the educational material for our intervention.

we will use the grounded theory for complete the analysis

Statistical Analysis for quantitative side : We assume that our study's CC-S HPV-Vax uptake rate would increase by 10% post-intervention. Based on a power analysis assuming the use of the student T-test to assess the difference in outcome between the intervention and control groups. The target sample size is estimated based on the G power software sample size calculator for the minimal sample size needed for an unlimited population size using a confidence interval of 80%, a standard deviation of 0.5, and a margin of error of 5%. The study requires 10 participants for intervention to test the feasibility of the program.

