**See the help text for additional guidance**

**1. A statement explaining the study design**

**Study Design:**

The proposed study consists of two parts.

Part 1 involves formative research through a focus group to gather insights and reach saturation.

Part 2 is a single-arm pre and post-test trial with the objective of evaluating the efficacy of an educational interventional program.

The study aims to increase cervical cancer screening (CC-S) and HPV vaccine (HPV-Vax) rates among Muslim American women (MAW) in Virginia, leading to a reduction in cervical cancer (CC) incidence and mortality.

2. A detailed description of all the procedures that will be followed to carry out the study, preferably in sequential order, and in sufficient detail that the study's methods could be replicated.
  - a. Part 1 - Formative Research: Conduct a focus group with 10 participants until saturation is reached.
  - b. Part 2 - Single-arm Pre and Post-test Trial: Enroll 20 participants to evaluate the educational program's effectiveness.

Participants will complete a baseline survey to assess their knowledge, attitudes, CC-S and HPV-Vax practices, and predisposing factors.

The survey will cover topics such as CC knowledge, experiences of medical mistrust, discrimination, spiritual coping, and fatalism.

3. The schedule and frequency of when and how procedures will be conducted (e.g. in person, online, phone, paper, etc.)

All procedures will be conducted in person at the Islamic Centers, except for follow-up phone calls.

Recruitment will occur during regular Friday prayers and religious holidays.

Participants will receive a brochure explaining the study and be screened for eligibility by the Research Assistant (RA). Eligible participants will be given a telephone contact for enrollment at a more convenient time.

The consent process will involve verbal explanation, providing the consent form in English, and allowing participants to ask questions. Follow-up surveys and confirmations will be conducted via phone calls.

4. A description of all research measures/tests/interventions that will be used, including analyses/tests conducted on specimens/biological samples (if applicable)

**Power Analysis:** No power analysis for this study. A target sample size of 20 participants has been determined based on PhD committee, the purpose of the project is training for the STUDENT.

Measures: Validated scales and surveys will be used to measure

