The primary outcome in increase the number of women who undergo cervical cancer screening. Secondary outcomes include an increase in knowledge and awareness, an increase in self-efficacy, and improvement in attitudes towards cervical cancer prevention.

Long-term outcomes include a reduction in cervical cancer incidence and mortality, sustainability of behavior change, and a reduction in healthcare costs associated with advanced-stage cancer treatment.

Moderator factors that can influence the effectiveness of the program include age, education level, ethnicity, socioeconomic status, Mediating mechanisms that explain how the program leads to its outcomes include improved knowledge and awareness, increased self-efficacy, attitude change, increased and social support,

Identifying and addressing moderator factors and mediating mechanisms can help to tailor the program to the specific needs and preferences of the target population and maximize its effectiveness

**Key Study Variables:** Socio-demographic variables, cultural/religious practices, cancer literacy, knowledge, perceived risk, barriers, benefits, and participation in preventive measures.

**Evaluation Measures:** Intervention acceptance will be self-reported, covering challenges, barriers, facilitators, likes/dislikes, and suggestions for improvement.

This study aims to address barriers to CC prevention among MAW through an educational intervention, using a sequential approach of formative research and a single-arm trial. The study will be conducted at Islamic Centers, involving in-person procedures, phone follow-ups, and self-report measures. The proposed methods are designed to evaluate the effectiveness of the educational program and its impact on CC-S and HPV-Vax rates in the target population.

**Statistical Tests:** Statistical tests such as t-tests or ANOVA can be used to analyze the data from the pre-post survey. These tests will help determine whether there are statistically significant differences between the pre- and post-survey results and whether the intervention had a significant effect on participants' knowledge and acceptance of cervical cancer prevention.

**7. \* The IRB only reviews research activities, so indicate for each of the study activities described in the question above or in the protocol which activities are:**

- Being performed exclusively for research purposes (i.e. they would not otherwise be done apart from this study) **VERSUS**.

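### Two stated conclusions exceed the single-arm design: attributing pre-post change in knowledge and acceptance to the programme, and measuring its impact on screening and HPV vaccination rates

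*Combined protocol and SAP*

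**What the plan says.** Study Procedures, question 6, describes Part 2 as a "single-arm pre and post-test trial with the objective of evaluating the efficacy of an educational interventional program". Its Power Analysis paragraph states "No power analysis for this study" and adds: "A target sample size of 20 participants has been determined based on PhD committee".

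Later in the same answer there are two separate claims.

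- **The Statistical Tests paragraph.** It names t-tests or ANOVA for the pre-post survey. The outcomes it has in view are what the women know about preventing cervical cancer and how far they accept it. The tests are meant to answer whether "there are statistically significant differences between the pre- and post-survey results and whether the intervention had a significant effect on" those outcomes.
- **The paragraph before it.** The proposed methods are "designed to evaluate the effectiveness of the educational program and its impact on CC-S and HPV-Vax rates in the target population".

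Other places bear on how these are read.

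- Aim 2 is called a test of preliminary efficacy. It is also given an ORBIT Phase III efficacy label in Background, question 3, and in Study Procedures, questions 1 and 2.
- Background, question 4, says the effectiveness of educational programmes in conservative communities could be assessed.
- The primary outcome is awareness of prevention methods in Background, question 3, and in Study Procedures, question 2. Under Outcomes in Study Procedures, question 6, it is the number of women screened.

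**The concern.** A test on pre and post scores addresses one question: did the scores change? The Statistical Tests paragraph adds a second, whether the intervention caused the change. In a single arm, any programme effect is mixed with whatever else differs between the two surveys.

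Such influences are plausible here. Outcomes are self-reported, the programme is supported by the mosques the women attend, the Imam introduces the research, and the research assistant belongs to the same community. Women also answer many of the same scales twice.

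The rates claim fails for different reasons: how the women are sampled, how uptake is measured, when it is measured, and how many women there are.

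At stake is what the study may conclude. Under the present wording, a significant change in knowledge score could be read as a programme effect, and a few newly screened women as an impact on rates in the target population.

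**Working it through.** **1. The plan's own figure.** Study Population, question 3, gives the only sample size that comes with inputs: "The study requires 10 participants for intervention to test the feasibility of the program", "using a confidence interval of 80%, a standard deviation of 0.5, and a margin of error of 5" per cent. The usual precision formula is n = (z × SD / margin)². At two-sided 80% confidence this gives (1.2816 × 0.5 / 0.05)² = 164. One-sided 80% gives 71 and two-sided 95% gives 384. None gives 10, and the target of 20 has no calculation to check. So no stated sample-size argument supports either claim.

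**2. What a pre-post test can show.** Assumptions, since the plan states neither: paired t-test, two-sided alpha 0.05. For a true mean change of d (in SDs of the change score), the statistic is non-central t with n − 1 degrees of freedom and non-centrality d√n. With n = 20 the critical value is 2.093. At d = 0.66 the non-centrality is 0.66 × √20 = 2.95 and power is 80%. With 16 pairs (80% of 20, the boundary of the retention target), d must be 0.75. A large change in score is therefore detectable.

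**3. What it cannot show.** Write the expected change as τ + b, where τ is the programme effect and b is everything else. The test concerns τ + b. One arm gives no separate information on b, so τ is not identified. To illustrate, set τ = 0 and assume values for b:

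| Assumed b (SD of change) | P(significant), 20 pairs | P(significant), 16 pairs |
|---|---|---|
| 0 | 5% | 5% |
| 0.2 | 14% | 12% |
| 0.3 | 25% | 20% |
| 0.5 | 56% | 46% |

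More women do not help. With b = 0.3, 40 pairs (non-centrality 0.3 × √40 = 1.90) give 46%, and 100 pairs (non-centrality 3.0) give 84%. The cause is the missing control group.

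**4. Rates in the target population.**

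- *Sampling.* Study Population, question 3, specifies a convenience sample, which does not support a statement about population rates.
- *Measure.* The uptake examples in Study Procedures, question 6, ask whether a woman has ever had a Pap smear or the HPV vaccine. That answer changes only if a first event occurs between surveys.
- *Timing.* Study Procedures, question 4, places the survey at month 0 after the educational material. Question 6 mentions follow-up surveys by phone without a time point. No interval is stated in which uptake could occur.
- *Size.* If no one reverts, exact McNemar needs six women changing: five give 2 × 0.5⁵ = 0.0625, six give 2 × 0.5⁶ = 0.031. Study Population, question 3, assumes a 10% rise in uptake, read here as 10 percentage points. Power is then P(X ≥ 6) for X ~ Binomial(20, 0.10) = 1.1%, or 0.3% with 16 women. Reversion of up to 10% raises the figure for 20 women to at most 4.5%. Power of 80% needs about 37% of the 20 newly screened. An observed 2 of 20 has an exact 95% CI of 1.2% to 31.7%.

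**The case against.** The plan is more modest elsewhere. Aim 2 speaks of preliminary efficacy, H1 predicts improvement after the intervention, Aim 3 calls the study a single-arm pilot, and the Power Analysis paragraph states a training purpose. The analysis text in Study Population already promises confidence intervals for all point estimates. The application form also asks for language that non-scientists can follow. This stands as context. It does not supply the missing caveat: none of these places says that change cannot be attributed to the programme, and the Phase III efficacy label pulls the other way.

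Five stronger readings are tempting, and the documents do not support them.

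- *The t-tests are said to show impact on rates.* They are not. The test sentence covers knowledge and acceptance only; the rates wording is a separate statement about the methods.
- *Any p below 0.05 will be reported as efficacy.* The plan sets no alpha, success criterion or reporting rule. The wording permits that reading but does not prescribe it.
- *The 14%, 25% and 56% are inflated type I error, or a result of having only 20 women.* In those scenarios scores really do change, so rejecting no change is correct. The error lies in the attribution, and the percentages rise with more women.
- *Twenty women can show nothing.* Step 2 shows otherwise for a large change in score.
- *There is a comparison group after all.* Background mentions a two-arm design, Study Population a control group, and Study Procedures, question 4, both groups. The Study Design text, Aim 3 and the closing paragraph of question 6 all say single arm. The remnants need reconciling; they do not describe a comparison the study will make.

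**Conclusion.** The point holds, as two separate overstatements in Study Procedures, question 6.

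Attribution of change in knowledge and acceptance fails because there is no control group. That conclusion rests on the design alone. The probabilities in step 3 only illustrate it, using assumed shifts, a paired test and two-sided alpha 0.05, none of which the plan gives.

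The claim about rates fails on sampling, measure, timing and size together. The 1.1% power figure assumes that the 10% rise means 10 points and that no one reverts.

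This should be corrected because it changes what the study may conclude. It is not a case for a control arm or a larger sample in a training pilot.

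**What to change.** 1. **Study Procedures, question 6, Statistical Tests.** Replace the claim with wording such as: *A paired analysis will estimate the mean within-woman change in knowledge and acceptance from pre to post, with a 95% confidence interval. Without a control group the change cannot be attributed to the intervention. Screening and vaccination uptake will be described only.*
2. **The rest of question 6** (Study Design, the enrolment line for Part 2, and the paragraph before Statistical Tests). Replace efficacy, effectiveness and impact on rates in the target population with *preliminary pre-post change among participants*.
3. **Aligned text.** Bring Background, question 4, and the Phase III efficacy label (Background, question 3; Study Procedures, questions 1 and 2) into line.
4. **Primary outcome.** Reconcile awareness (Background, question 3; Study Procedures, question 2) with number screened (Study Procedures, question 6), so that it is clear which result the conclusion rests on.

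No participants, visits or data are added. The cost is a less favourable stated conclusion.

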## PROMIS WOMAN Education Program : ImProving ceRvical cancer preventOn methods among Muslim Americans WOMEN

### Project Details

An intervention includes both physical procedures by which information or biospecimens are gathered (e.g., venipuncture) and manipulations of the subject or the subject's environment that are performed for research purposes.

An interaction includes communication or interpersonal contact between investigator and subject. It may include in-person, online, written, or verbal communications.

Secondary information/biospecimens are information or biospecimens that have been or will be collected for some other "primary" or "initial" activity and that will be used secondarily in the research study.

**1. \* Select all of the following types of interventions that apply to this study (selections will branch):**

 **Social/Behavioral interventions or experimentation / Tasks / Environmental manipulations**

- Deception (misleading participants through false or incomplete information)
- Drug(s) / Biologics / Supplement(s) / Other Compounds (investigational products or products whose administration is dictated by the study protocol and not per the physician's clinical judgment)
- IV contrast administration for research-related imaging (will branch to the Drugs page)
- Placebos
- Safety and/or effectiveness evaluation of Bio-Medical Device(s), including in-vitro diagnostic devices/assays, mobile medical apps, software functions, and HUDs used in clinical investigations
- Washout Periods
- Expanded Access – Treatment Use of an Investigational Product
- Medical or Surgical Procedures (eg: physical exam, clinical procedures, scans, etc)
- Specimen/biological sample collection
- None of the Above

**2. \* Select all of the following types of interactions and methods of data collection that apply to this study (selections will branch):**

- Surveys / Questionnaires /Written responses to questions (including data entry)
- Active Internet data collection (i.e. using the internet to collect data, including online surveys, data collection via Zoom, apps, etc.)
- Passive Internet data collection (i.e. passively observing online behavior, bots)
- Interviews / Focus Groups / Verbal responses to questions
- Audio / Video recording or photographing participants
- Observations
- Educational Settings/Assessments/Procedures
- None of the Above

**3. \* Select all types of recordings that will be made:**

- Audio
- Video
- Photographs

**4. \* Describe the purpose of the recordings, who will be recorded and when such recordings will occur:**

Part 1:

The recordings in Part 1, which involve the focus group interviews, are for analysis purposes. The audio recordings will be used to transcribe the data and analyze the transcripts. The research assistant conducting the interviews will record the sessions using a VCU iPad. The interviews will take place in the private room provided by the mosque. It's important to note that the research assistant will not use any names or identification during the interviews to ensure confidentiality.

Part 2:

In Part 2, the recordings serve a different purpose. During the education sessions, photos will be taken as part of the community outreach work. These photos will be used exclusively for conference purposes to disseminate the findings of the study. Similar to Part 1, the research assistant will use a VCU iPad to record the sessions, but no identifying information will be used or captured during the interviews.

the recordings are used to facilitate analysis in Part 1 and for dissemination purposes in Part 2. They are conducted using a VCU iPad in the private room provided by the mosque, and precautions are taken to ensure confidentiality and anonymity of the participants.

**5. \* Select all types of secondary information and/or specimens that apply to this study (selections will branch):**  
**See the help text for definitions.**

- Individually Identifiable Health Information (PHI)
- Secondary data/specimens NOT from a research registry or repository
- Information/specimens from a research registry or repository (Usage Protocol)
- Information/specimens originally collected for a previous research study
- Publicly available information/specimens
- Government-generated or collected information that was or will be obtained for nonresearch activities [only applicable to research conducted by or on behalf of a Federal department or agency]
- No secondary data/specimens will be used**

## PROMIS WOMAN Education Program : ImProving ceRvical cancer preventOn methods among Muslim Americans WOMEN

### Behavioral Intervention/Task Details

This page asks for details about the social/behavioral intervention, task, or environmental manipulation in the research.

Interventions include both physical procedures by which information is gathered and manipulations of the subject or the subject's environment that are performed for research purposes. This might include activities such as playing computer games, performing a task, thought/cognition activities, environmental manipulations, and educational activities.

If the study only involves surveys, interviews, or secondary data collection, go back to the Project Details page and uncheck "Social/Behavioral interventions or experimentation / Tasks / Environmental manipulations" in Question 1.

**1. \* Describe the duration of the social/behavioral intervention, task, or environmental manipulation:**

The event will be organized for three hours.

-The education sessions will be 1.5 hours ( 90 minutes).

- The self-report survey will take 45 minutes.

- The rest of the time, we will have a break and lunch.

The education sessions will be offered on Saturday and Sunday.

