**See the help text for additional guidance.**

The principal investigator (PI) has a community partnership with the Islamic Center of Richmond, where the research team will distribute flyers about the project (see attachment). The research team will be present at the Mosque at predetermined times where women could approach study team members to ask questions, sign up for participation, and schedule appointments.

1) Identification of potentially eligible participants:

- The research team will distribute flyers about the project at the Islamic Center of Richmond to identify potentially eligible participants.
- The education material will be mentioned as PDF in the docs section

2) Recruitment procedures to invite participation in the study:

Place: The research team will be present at the Mosque during predetermined times.

Participants: Women interested in participating can approach study team members to ask questions, sign up for participation, and schedule appointments.

Written recruitment materials, such as flyers, will be distributed to provide information about the study.

Verbal recruitment materials will be used when study team members interact with potential participants.

The research assistant will handle contact with potential participants, including scheduling interviews and baseline surveys.

Recruitment procedures will take place at the Islamic Center of Richmond.

3) Eligibility screening prior to consent and how those activities will be carried out:

During these interactions, eligibility screening will be conducted to ensure participants meet the study criteria.

The research team will use a standardized screening tool or questionnaire to assess eligibility.

For focus group meetings, participants will be screened for eligibility before being scheduled for interviews.

For the one-arm clinical trial, participants will be screened for eligibility during the scheduling of baseline surveys.

The education materials will be clearly outlined in the study plan PDF.

The survey will be given to the potential participants in person ( hard) or through QR code through redcap.

Summary the intervention :

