The intervention group will consist of 20 participants who will receive one education session divided into three sections/videos. The session will be offered in a single day and last 1.5 hours. The session will include the following topics: 1) Risk of HPV infection (30 minutes), 2) Cervical cancer risk (30 minutes), and 3) Advantages and benefits of early screening and the HPV vaccine (30 minutes).

All participants from both groups will be given the survey at month 0 (baseline) after the delivery of the educational material. The survey will be self-report, available in both hard copy and electronic form with a QR code for Redcap.

Participants are expected to take approximately 45 minutes to complete the survey.

The Islamic center offer private room to practice the research activities in both phases ( Focus group and single arm trial)

**5. \* Does this study have a separate protocol document (i.e. a multisite or sponsor's protocol) that contains a detailed description of the study's methodology?**

Yes

No

**6. \* Since a separate protocol document is not uploaded, describe the proposed research using language understandable to those IRB committee members whose expertise is not scientific. The description must include:**

- 1. A statement explaining the study design**
- 2. A detailed description of all the procedures that will be followed to carry out the study, preferably in sequential order, and in sufficient detail that the study's methods could be replicated**
- 3. The schedule and frequency of when and how procedures will be conducted (e.g. in person, online, phone, paper, etc.)**
- 4. A description of all research measures/tests/interventions that will be used, including analyses/tests conducted on specimens/biological samples (if applicable)**

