Age: Age can be measured using a simple demographic question such as "What is your age?" in the pre- and post-intervention surveys.

Education: Education level can be measured using a simple demographic question such as "What is the highest level of education you have completed?" in the pre- and post-intervention surveys.

Modesty and Conservatism: can be measured using a combination of demographic questions and attitudinal scales.

For example, demographic questions could include "How important is modesty in your culture?" or "How conservative would you describe yourself?" while attitudinal scales could include items such as "I am comfortable discussing reproductive health issues with my healthcare provider" or "I am willing to discuss cervical cancer prevention activities with my family and friends."

Cervical Screening and HPV Vaccine Uptake: can be measured using self-reported questions such as "Have you ever had a Pap smear?" or "Have you ever received the HPV vaccine?" in the pre- and post-intervention surveys. Additional questions can also be included to determine the frequency and timing of screening and vaccine uptake.

Participants' Knowledge and Attitude: can be measured using a combination of open-ended and closed-ended questions.

Open-ended questions could include "What do you know about cervical cancer prevention activities?" while closed-ended questions could include "Do you believe that cervical cancer screening is important?" or "Do you believe that the HPV vaccine is safe and effective?"

Feasibility of Intervention: can be measured by tracking enrollment rates, attendance rates, and completion rates in the pre- and post-intervention surveys.

Additional questions can also be included to assess the overall acceptability of the intervention among participants.

Self-efficacy: can be measured using a self-efficacy scale specific to cervical cancer screening, such as the Cervical Cancer Screening Self-Efficacy Scale (CCSES), as described in the previous answer.

Acceptability of the Program: can be measured using a satisfaction survey at the end of the intervention program. The survey could include questions such as "Did you find the program useful?" or "Would you recommend this program to a friend?"

Outcomes:

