**1. Total Monetary Amount:**

- Focus Group (Part 1): Each participant in the focus group will receive a total compensation of \$150 (\$75 for each session) for their involvement in two sessions.
- Intervention (Part 2): Participants in the intervention group will receive \$150 for completing both the pre and post-surveys ( \$75 for each survey)
- Satisfactory Survey Compensation: Participants who complete the survey will receive \$50 as compensation.

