**When and Where Consent Will Occur:**

Consent for the intervention group will be obtained at the Islamic Center during the scheduled education sessions. Participants will have the opportunity to provide consent before engaging in the educational program.

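### The sections on consent, survey timing and the event timetable conflict; followed literally, they provide no consented pre-test before the teaching

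*Combined protocol and SAP*

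**What the plan says.** The documents describe the timing of consent and surveys in several places.

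- **Event timetable** (Behavioral Intervention/Task Details, Question 1). The event lasts three hours and the teaching takes 90 minutes. "The self-report survey will take 45 minutes". Then: "The rest of the time, we will have a break and lunch". The same answer adds: "The education sessions will be offered on Saturday and Sunday".
- **Design and payment.** Study Procedures, Question 6, describes a single-arm pre-test and post-test trial in 20 women. Compensation, Question 1, pays $150, as $75 per survey, "for completing both the pre and post-surveys", and a further $50 for a satisfaction survey. Under Measures in Question 6, acceptability "can be measured using a satisfaction survey at the end of the intervention program".
- **Consent** (Consent Groups, Intervention group consent form). Question 7: "Consent for the intervention group will be obtained at the Islamic Center during the scheduled education sessions". Signed consent is selected and no waiver is requested. Question 8 selects a mandatory wait at home before signing, and Question 10 expects a decision time of one to two weeks.
- **Baseline contact** (Study Procedures, Question 4, item 3). For the trial, "participants will be screened for eligibility during the scheduling of baseline surveys". The research assistant schedules these surveys, which may be done on paper or through a REDCap QR code.
- **Intervention summary** (end of Study Procedures, Question 4). "The session will be offered in a single day and last 1.5 hours". It describes one survey, labels it the month 0 baseline, and places it after the educational material has been delivered.
- **Follow-up** (Study Procedures, Question 6, item 3). Everything is done in person except follow-up phone calls, and follow-up surveys are by phone. No date is given.

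**The concern.** H1 is a claim about change in knowledge and acceptance, so each woman needs one measurement before the teaching and one after. The timetable has a single survey slot and does not say which survey fills it. The consent section ties signed consent to the session. That rules out a consented survey at an earlier appointment, unless the section is amended. The intervention summary then puts the survey it calls baseline on the wrong side of the teaching. If staff worked from those three places, the only event-day survey would be a post-teaching one carrying a baseline label, with no untaught score to compare it with. In a single-arm trial there is no control group to fall back on, so H1 could not be tested.

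**Working it through.** **1. The plan's own timetable.** Inputs from Behavioral Intervention/Task Details, Question 1: event 180 minutes, teaching 90, survey 45. The teaching figure agrees with the three 30-minute topics in the intervention summary: 3 x 30 = 90.

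- Remainder: 180 - 90 - 45 = 45 minutes for break and lunch. The timetable closes, so there is no arithmetic error.

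**2. Both surveys at the event.** The intervention summary gives about 45 minutes per survey.

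- Remainder: 180 - 90 - 2 x 45 = 0 minutes for break, lunch, satisfaction survey and consent.

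It is unlikely that the 45 minutes covers both surveys. Both places speak of one survey, the two are paid separately, and Study Procedures, Question 2, lists 11 scales for the pre-test and 11 for the post-test.

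**3. Items with no stated length.** Assumed ranges: satisfaction survey 5 to 15 minutes, consent 0 to 30, break and lunch 0 to 45.

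- Both surveys at the event: from 90 + 90 + 5 + 0 + 0 = 185 to 90 + 90 + 15 + 30 + 45 = 270 minutes, which is 5 to 90 over.
- One survey elsewhere: from 90 + 45 + 5 + 0 + 0 = 140 to 90 + 45 + 15 + 30 + 45 = 225 minutes, which is 40 spare to 45 over. It fits if the satisfaction survey, consent and break together take 45 minutes or less.

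So the event works with one survey and fails with two. What matters is where the other survey goes.

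**4. The sections side by side.**

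| Step | One section | Another section |
|---|---|---|
| Consent | At the education session (Consent Groups, Question 7) | After a wait at home, one to two weeks expected (Questions 8 and 10) |
| Pre-test | At a scheduled baseline survey (Study Procedures, Question 4, item 3) | Survey called baseline given after the teaching (intervention summary) |
| Post-test | Survey after the teaching, but labelled baseline (intervention summary) | Follow-up surveys by phone, undated (Question 6, item 3) |
| Session days | Saturday and Sunday (event timetable) | A single day (intervention summary) |

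**5. The literal reading.** Consent is signed at the session, so no consented survey can come earlier. On the day, a woman may consent before the teaching starts, which in principle allows a pre-test then. But the timetable has one survey slot, and the intervention summary places that survey after the teaching. The number of consented pre-tests before teaching is therefore 0 of 20.

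**The case against.** The strongest reply is that nothing requires both surveys to fit inside the event. Question 1 of the behavioral section asks how long the intervention lasts, so its silence about other contacts is not a contradiction. Study Procedures has baseline surveys scheduled by the research assistant, completion by QR code, and follow-up surveys by phone. Either route leaves one survey at the event, which is what the timetable allows. This reply stands, and it limits the point in three ways.

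- A reader might infer that one outcome measurement is bound to be rushed or lost. The documents do not support that, because they describe survey contacts outside the event.
- A reader might infer a definite overrun of the three hours. Any such figure needs both surveys on site and lengths that the documents do not give; with one survey elsewhere the day can fit.
- A reader might infer that women attending on Sunday would be pre-tested after hearing from those taught on Saturday. The documents do not say that there are two groups, how women would be split, or that pre-tests are taken on the day. Offering sessions on both days could simply mean available dates. No size of bias can be derived.

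The reply does not remove the conflict, because each route out contradicts another section. An earlier baseline survey would come before the consent that Question 7 takes at the session. A phone post-test would have no stated date, would differ in mode from a self-completed pre-test, and would leave unexplained why the survey after the teaching is called baseline.

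**Conclusion.** The point holds as a conflict between sections, and it is more than missing detail. The timetable is arithmetically sound but holds one 45-minute survey, and it gives no time to a second survey, the satisfaction survey or consent. Read literally with the consent section and the intervention summary, it yields no consented pre-test before the teaching for any of the 20 women, and the H1 change may then not be measurable. This is a risk, not a certainty: staff who relied on the scheduled baseline survey would obtain a pre-test, though before the point at which the plan takes consent. The conclusion rests on the stated 180, 90 and 45 minutes and on the wording of the sections. It does not depend on the assumed durations.

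**What to change.** Reconcile Study Procedures, Questions 4 and 6, Behavioral Intervention/Task Details, Question 1, and the intervention-group consent answers (Questions 7, 8 and 10) in one timed schedule giving the timing, mode and window of each survey.

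1. Take consent, after the decision time in Question 10, and then all 20 pre-tests at the scheduled baseline appointment. Complete them before the first session on either day. This also removes any doubt raised by the Saturday and Sunday wording, which should itself be clarified.
2. Amend the consent section to match, so that consent is no longer first taken at the education session.
3. Correct the intervention summary so that the survey after the teaching is the post-test for knowledge and acceptance, and not the baseline.
4. Use the event's single survey slot for that post-test, followed by the satisfaction survey. With the satisfaction survey assumed to take 5 to 15 minutes, 180 - 90 - 45 - 15 = 30 to 180 - 90 - 45 - 5 = 40 minutes remain for break and lunch.
5. Keep the phone follow-up for self-reported screening and vaccine uptake, and state its date. The same-day post-test must not replace it. Study Procedures, Question 6, names the number of women screened as the primary outcome, and that cannot change within a three-hour event.

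The cost is protocol wording and one earlier contact per woman, which Study Procedures, Question 4, already foresees. No additional participants are needed.
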